^c Data from 1 subject were excluded from summary statistics because R^2 was < 7

^d Data from 1 subject were excluded from summary statistics because the extrapolated portion of AUC was \geq 25%

^e Data from 2 subjects were excluded from summary statistics because the extrapolated portion of AUC was \geq 25%

^f Data from 3 subjects were excluded from summary statistics because the extrapolated portion of AUC was \geq 25%

Note: Study medication was administered IM.

PK parameters for Part 3 are presented in [Table 4](#). On Days 1 and 7, over the multiple dose range of 2.5 to 10.0 mg/kg, AUC from time 0 to the end of the dosing interval (AUC_{tau}) demonstrated dose proportionality; the increase in C_{max} with dose was modestly greater than dose proportional with the power model and consistent with dose proportionality with the ANOVA model.

Overall, there was an approximately 1.5-fold increase in exposure (AUC) with repeat dosing over 7 days. Assessment of trough concentrations of galidesivir suggested that steady state had not been achieved by Day 7.

Table 4: Study BCX4430-101 Part 3: Summary of Select Plasma Pharmacokinetic Parameters Following 7-Day, Multiple Ascending Intramuscular Galidesivir Regimens (Days 1 and 7)

PK Parameter	2.5 mg/kg Galidesivir N = 7		5.0 mg/kg Galidesivir N = 8		10.0 mg/kg Galidesivir N = 8	
	Day 1	Day 7	Day 1	Day 7	Day 1	Day 7
C _{max} (ng/mL) ^a	1820 (18.7) n = 7	2390 (39.0) n = 7	6840 (12.6) n = 8	6900 (17.4) n = 8	11400 (25.3) n = 8	17500 (83.3) n = 7
T _{max} (h) ^b	0.25 (0.08, 0.50) n = 7	0.25 (0.10, 0.52) n = 7	0.25 (0.25, 0.50) n = 8	0.25 (0.08, 0.25) n = 8	0.25 (0.25, 0.25) n = 8	0.25 (0.08, 0.50) n = 7
C _{tau} (ng/ mL) ^a	33.6 (23.9) n = 7	138 (19.1) n = 7	68.4 (15.9) n = 8	280 (17.8) n = 8	134 (15.7) n = 8	494 (16.6) n = 7
AUC _t (ng.h/mL) ^a	4830 (16.9) n = 7	15100 (16.1) n = 7	12100 (11.6) n = 8	32500 (11.5) n = 8	21600 (10.1) n = 8	62100 (13.9) n = 7
AUC _{tau} (ng.h/mL) ^a	4830 (17.0) n = 7	7620 (17.0) n = 7	12100 (11.6) n = 8	17600 (10.3) n = 8	21700 (10.1) n = 8	34500 (13.6) n = 7
t _{1/2} (h) ^a	NR	104 (15.9) n = 7	NR	85.7 (17.3) n = 8	NR	113 (26.4) n = 7

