Abbreviations: AUC_t = area under the concentration-time curve from time 0 to time “t”; AUC_{tau} = area under the concentration-time curve from time 0 to the end of the dosing interval; C_{max} = maximum concentration; C_{tau} = trough concentration; CV = coefficient of variation; max = maximum; min = minimum; IM = intramuscular; NR = not reported; PK = pharmacokinetic; QD once daily; t_{1/2} = half-life; T_{max} = time to C_{max}.

^a Data reported as geometric mean (CV% of geometric mean)

^b T_{max} reported as median (min, max)

Note: Galidesivir was administered QD IM with 20 mg of lidocaine over 7 days. NR = not calculated due to 24 hours not being a reliable time frame from which to estimate half-life and any related parameters. Lambda-based calculations truncated at the dosing interval were not summarized for Day 1.

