In the event that there are any unresolved safety findings that are ongoing at Day 21, the subject will be followed at additional study visits until the findings are resolved or stabilized. If it is determined that the median half-life is longer than anticipated following IV infusion, or if after obtaining PK data through 96 hours, the AUC_{inf} estimate is $> 25\%$ of the AUC from time 0 to the last measurable concentration of drug (AUC_{last}), serial PK sampling may be extended beyond 96 hours in subsequent cohorts, or additional samples may be added in the intervening period between discharge from the CRU and the final follow-up visit (Day 21).

Safety and tolerability will be evaluated through assessments of AEs, laboratory analyses (clinical chemistry, hematology, coagulation, urinalysis, CK-MB, troponin), vital signs, ECGs, ECHOs, cardiac telemetry, and PEs at the time points indicated in the schedule of assessments. PK parameters will be analyzed from the plasma and urine samples collected at the time points indicated in the schedule of assessments ([Table 5](#)).

Enrollment of subjects in each sequential higher dose level cohort will occur only after completion of a clinical safety review of laboratory, AE, vital sign, ECG (12-lead and telemetry), and PE data for all subjects up through 96 hours post-dose and plasma PK data through 24 hours, by the Sponsor medical monitor, clinical pharmacologist, and principal investigator (PI) at a dose escalation review meeting. Rules for halting the escalation to the next dose will be followed as defined in Section [7.6.3.2](#).

Safety and PK data for each cohort will be submitted to the US Food and Drug Administration (FDA) after each cohort is complete. Escalation to the next planned dose may proceed as long as the halting rules are not triggered as defined in Section [7.6.3.2](#).

Figure 1: BCX4430-106 Study Design

Abbreviations: D = day; PK = pharmacokinetic.

Table 5: Schedule of Assessments

Assessment	Screening	In Clinic (CRU) Study Period							Return to CRU for PK Sample	Follow-up or Early Termination Visit
		Day -28 to -2	Day -1 (Admission)	Day 1 Baseline (Pre-dose)	Day 1 (Post dose)	Day 2	Day 3	Day 4	Day 5 (Discharge)	Day 6, Day 8, Day 14 ⁿ
Informed consent	X									
Inclusion/exclusion criteria	X	X								
Medical history	X	X								
Weight/height/BMI	X	X ^a								
Drugs of abuse screen/urine alcohol test/urine cotinine screen	X	X								
HIV/HCV/HBV serology	X									

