11.5.2. Dose Escalation Committee

Following the completion of each cohort, the DEC will meet to decide if the required safety parameters have been met. All available safety data for all subjects in a given cohort through 96 hours and PK data through 24 hours post-dose will be reviewed by the Sponsor Medical Monitor, Clinical Pharmacologist, and PI and used in the decision to escalate to the next higher dose. Review meetings will be held following each dose level of Cohorts 1 to 4.

An interim Safety Summary Report will be prepared for review by the DEC that will document the following safety findings for each dose cohort:

- Demographics
- Dosing information, including any subjects who discontinued dosing
- Listing of any SAEs with assessment of severity
- Listing of AEs with assessment of severity
- Listing of any graded clinical chemistry findings

- Listing of all clinical chemistry findings Grade 2 or higher
- Listing of any graded hematology findings
- Listing of all hematology findings
- Listing of any graded urinalysis findings
- Listing of all urinalysis findings
- Listing of vital signs
- Listing of QT findings
- Telemetry findings
- Additional narrative summaries
- Listing of subjects who terminated early
- Listing of PE data

An interim PK report will be prepared for review by the DEC that will document the following PK findings for each dose cohort:

- Preliminary plasma PK parameters (through 24-hours post-dose) based upon nominal times: AUC; C_{max} , T_{max} , terminal elimination half-life ($t_{1/2}$; median, minimum, maximum, geometric mean, coefficient of variation [CV%])
- Predictions of C_{max} and AUC values for the next cohort, where relevant

The interim Safety Summary and PK report documents will form the basis of teleconferences involving the Sponsor and the PI to evaluate each completed cohort in the study. The DEC will use the Dose Escalation Criteria to determine whether escalation as planned per protocol may commence.

Dose Escalation Criteria

The study will proceed to the next planned dose level if **NONE** of the following is met:

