$\lambda_z$	Terminal elimination rate constant, estimate by linear regression of the terminal elimination phase of the concentration of drug versus time curve	Lambda_z from WinNonlin  If Rsq < 0.80 then parameter is flagged in listings and will not be used in summary statistics.
$V_z$	Volume of distribution of the drug	Vz_obs from WinNonlin  If valid $\lambda_z$ is not present, then parameter is flagged in listings and will not be used in summary statistics.
$T_{max}$	Time to $C_{max}$	Tmax from WinNonlin

Note: In all derivations of PK parameters, BQL values at the beginning of the profile will be set to zero, whereas BQL values that occur after the first quantifiable point will be considered missing. Samples that are BQL but are between two samples with detectable concentrations will be excluded from PK analysis.

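### The interim PK report asks for a terminal half-life from 24-hour data, a window the protocol itself calls unreliable, and the visible final-analysis screen would not catch such an estimate

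*Protocol*

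**What the plan says.** Protocol 11.5.2 lists the contents of the interim PK report for the Dose Escalation Committee. The list opens "Preliminary plasma PK parameters (through 24-hours post-dose) based upon nominal times" and names AUC, Cmax, Tmax and "terminal elimination half-life", with median, range, geometric mean and CV%. SAP 7.2 repeats it.

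The note to protocol Table 4 explains why the earlier intramuscular (IM) study reported no Day 1 half-life: "not calculated due to 24 hours not being a reliable time frame from which to estimate half-life and any related parameters".

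Protocol 7.1 gives two conditions under which PK sampling may be extended. One begins "If it is determined that the median half-life is longer than anticipated following IV infusion". The other concerns the extrapolated AUC, judged "after obtaining PK data through 96 hours". Neither the anticipated half-life nor the data window for the first condition is given.

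For the final analysis, the lambda_z row of SAP 16.1.1 reads: "If Rsq < 0.80 then parameter is flagged in listings and will not be used in summary statistics". The half-life, AUCinf and Vz rows depend on a valid lambda_z. The CL row carries no validity condition, and the extrapolated percentage is only listed. SAP 16.2.2 refers the choice of lambda_z points to an internal guideline, whose content is not reproduced.

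**The concern.** A terminal half-life needs samples well into the terminal phase. Here the first 24 h are dominated by distribution and early clearance, so a slope fitted to them is too steep and the half-life too short. Two things are at stake.

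- **Interim.** The only interim half-life that the plan defines comes from a window that biases it downwards, while one extension condition asks whether half-life is longer than expected. Judged on that value, the condition could be missed.
- **Final.** Half-life, AUCinf, CL and Vz are secondary-endpoint parameters, and AUCinf enters the dose-proportionality analysis. With six active subjects per cohort, one subject sampled only to 24 h could shift a cohort summary if nothing in the lambda_z rule removes that subject.

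**Working it through.** **1. Reproduce the reported half-life.** The Cohort 2 dose-escalation summary appended to the SAP (10 mg/kg IV, geometric means) gives half-life 89.1 h, CL 285 mL/h/kg, Vz 36,600 mL/kg, Cmax 9,240 ng/mL, AUC0-24 20,400, AUC0-last 30,200 and AUCinf 32,400 ng.h/mL, with 11.1% extrapolated. Half-life = ln 2 × Vz/CL = 0.693 × 36,600/285 = 89.0 h, which agrees.

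**2. What data lie behind it?** AUC0-last/AUC0-24 = 30,200/20,400 = 1.48, so samples after 24 h were used. The extrapolated area is 0.111 × 32,400 = 3,596, so the last concentration is about 3,596 × 0.693/89.1 = 28 ng/mL. With mono-exponential decline after 24 h, the concentration at 24 h is (32,400 − 20,400) × 0.693/89.1 = 93 ng/mL. The last sample is then near 24 + (89.1/0.693) × ln(93.4/28.0) = 179 h. Taking the post-24-h area instead as 30,200/0.889 − 20,400 = 13,570 gives about 189 h. The two areas differ because the geometric means are not fully consistent with one another; for example, Dose/AUCinf = 10,000,000/32,400 = 309 against the stated CL of 285. The means may rest on different subject sets.

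**3. Window against half-life.** Half-lives are 73.2 to 85.4 h after single IM doses of 1.8 mg/kg and above (Table 3), and 85.7 to 113 h on Day 7 (Table 4). A 24-h window covers 24/113 = 0.21 to 24/73.2 = 0.33 of one half-life.

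**4. One worked profile (assumed).** The IV concentrations at 8 to 24 h are not given, so a profile must be assumed. Take:
- 134 ng/mL at 24 h (the IM 10 mg/kg Day 1 trough in Table 4)
- 80% of it (107.2) terminal, with half-life 89.1 h
- 20% of it (26.8) in an intermediate phase with half-life 5 h.

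Then C(t) = 107.2 × 2^((24−t)/89.1) + 26.8 × 2^((24−t)/5), which gives 259, 195 and 134 ng/mL at 12, 16 and 24 h. The log-linear slope through these points is 0.0538 per h:
- Apparent half-life = 0.693/0.0538 = 12.9 h, so the true value is 89.1/12.9 = 6.9 times longer.
- R-squared = 0.99, which passes the 0.80 screen.
- AUCinf = 20,400 + 134/0.0538 ≈ 22,900. The profile's own value is 20,400 + 13,970 = 34,370, so the estimate is 33% low.
- Extrapolated share = 2,490/22,890 = 11%. The 25% cut-off used in the IM study would not catch it either.

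**5. Range over assumed profiles.** Tri-exponential 1-h-infusion curves were matched to Cmax 9,240 and AUC0-24 20,400, and kept if the post-24-h area was 11,000 to 14,500. Assumed ranges: concentration at 24 h 115 to 150 ng/mL, true half-life 73.2 to 113 h, terminal share of the 24-h concentration from 0.5 or 0.7 up to 1.0, intermediate half-life 3.5 to 12 h.

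| Quantity, 12 to 24 h fit | Range | Median |
|---|---|---|
| True/apparent half-life | about 1.1 to 14 | about 3 (share from 0.7) to 5 (share from 0.5) |
| R-squared | at least 0.96 | – |
| AUCinf shortfall | about 3 to 38% | 27% |

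The upper end of the ratio moves between about 11 and 15 with the ranges chosen. An 8 to 24 h fit passes the R-squared screen in about 97% of curves. Bi-exponential curves give smaller ratios: 1.1 to 1.7 for a 12 to 24 h fit and 2.2 to 6.1 for 8 to 24 h. Three Cohort 2 subjects exceeded the assay's upper limit, so Cmax may be slightly low; that mainly affects the early part of the curve.

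**6. How far does 96 h go?** With mono-exponential decline after 24 h, the area beyond 96 h is 12,000 × 2^(−72/89.1) = 6,850, or 21% of 32,400. A 96-h minimum is far better than 24 h but needs its own justification.

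**The case against.** The case that this is a minor wording matter is substantial.

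- **A reader might infer a fixed multiplier, such as 7 to 10 times too short.** The documents do not support one. It depends on unreported 8 to 16 h concentrations and an assumed intermediate phase. In the set of curves with terminal share from 0.7, only about 10% fall in that band.
- **A reader might infer that the half-life trigger can never fire.** That does not follow. The trigger names no data window, its alternative uses 96-h data, and protocol 11.2.1 separately lets sampling times change in the light of early cohorts. Samples on Days 6, 8, 14 and 21 are already scheduled. The trigger is also permissive, so missing it would cost little.
- **No escalation decision rests on half-life.** The only PK criterion is median AUC24, which 24-h data support.
- **Practice was sound in Cohort 2.** Later samples were used, and half-life and clearance from the subject with 24-h data only were left out of the means if that subject was on active drug. The 24-h cut may have been read as a minimum.
- **A reader might infer that a 24-h-only subject will certainly distort the final summaries.** That is unproven. The cited lambda_z guideline may exclude such a profile. The case should also be rare, since subjects stay in the unit to 96 h, and the evaluability rule in protocol 8.5 governs replacement rather than entry to these summaries.

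All of this stands and limits the consequences. It does not remove the contradiction between the interim list and the Table 4 note, or the absence of any visible duration condition in the SAP. The Cohort 2 handling shows that the list, followed literally, would not have given a usable value. The Table 4 note concerns IM dosing, but its reasoning carries over to an IV half-life of 89 h.

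**Conclusion.** The point holds in a limited form. The interim list asks for a terminal half-life from a window that the protocol calls unreliable and that covers about a fifth to a third of one half-life. The direction of the bias is clear: too short. Its size is not fixed by the documents. For a 12 to 24 h fit it is a factor of about 1.1 to 14, with median about 3 to 5, under tri-exponential profiles matched to Cohort 2. Such a value is a poor basis for the half-life trigger, which also lacks a stated data window and an anticipated value.

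On the same assumptions, the R-squared screen would pass a 24-h-only profile with AUCinf about 3 to 38% low. Whether that would happen in the final analysis depends on the guideline that is not shown. Nothing here questions the 89.1 h reported for Cohort 2 or the AUC24 escalation criterion.

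**What to change.** - **Protocol 11.5.2 and SAP 7.2:** remove half-life from the 24-h list, or report it only from subjects with later samples, as was done in Cohort 2.
- **Protocol synopsis and 7.1:** state that the half-life trigger is judged on those later data, and give the anticipated half-life a value.
- **SAP 16.1.1:** add a minimum sampling duration to the lambda_z validity rule, for example samples to at least 96 h, with the choice justified against the observed half-life. Apply it to half-life, AUCinf, Vz and CL; the CL row currently has no condition. If the cited guideline already contains such a rule, state it in the SAP.

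The cost is wording in both documents. An occasional subject with short sampling would drop out of those four summaries, and out of the AUCinf dose-proportionality analysis if the same flag is applied there. Cmax and AUC24 are unaffected.

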11.5.3. Safety Monitoring Committee

A SMC will be assembled for this study. The SMC membership is determined by NIAID, who is also responsible for the Charter. The SMC will review reports provided by the PI and Sponsor as outlined in the Charter and agreed upon in the organizational meeting.

The SMC will meet to review all available safety and PK data from the study on the following occasions: when study halting criteria are met, when dose escalation could not be approved by the DEC, or when the criteria for not dosing additional subjects in a cohort are met after the sentinel subjects are dosed. A final SMC meeting will occur approximately 6 to 8 months following clinical database lock to review the cumulative unblinded safety data for the study.

Data for all SMC meetings will be provided in a standard summary format. The SMC may be asked to provide recommendations in response to questions posed by DMID. Additionally, following the administration of Cohort 4 and a review of the PK and safety data by the SMC, the Sponsor may make a recommendation to enroll additional cohorts in the SAD to further characterize the safety, tolerability and PK of galidesivir. This additional enrollment will only occur provided that the PK is increasing predictably in proportion with increasing dose, no safety concerns have arisen or stopping criteria have been met, the exposure is below the NOAEL exposure identified in NHP studies, and with recommendation by the SMC. The protocol will be amended to enable the enrollment of any SAD cohorts after Cohort 4.

The recommendations and final minutes of any SMC meeting will be supplied to the Sponsor, FDA and IRB, as applicable.

12. STATISTICS

12.1. Study Hypothesis

No formal study hypothesis will be stated or tested in this Phase 1 study.

12.2. Sample Size Considerations

No formal power or sample size calculations were used to determine cohort sizes. Cohort sizes were based upon experience in other SAD Phase 1 studies. A sample size of 6 subjects receiving

active drug per cohort should provide adequate characterization of PK and safety assessments within this setting.

12.3. Final Analysis Plan

12.3.1. Statistical Methods

A detailed Statistical Analysis Plan (SAP) will be developed and finalized prior to database lock. The SAP will describe the methods of analyses/summaries, including all endpoints, time points, populations, missing data, etc. Any deviation from the analyses outlined in the SAP will be described in the final CSR.

12.3.1.1. Analysis Populations

The analysis populations are defined below. Data from placebo-treated subjects will be pooled across cohorts.

Safety Population

The safety population will include all randomized subjects who received any amount of study drug (ie, a partial infusion). Subjects will be analyzed according to the treatment received. This population will be used for all analyses of accountability, demographics, galidesivir drug concentration, and safety.

Pharmacokinetic Population

The PK population will include all subjects for whom PK parameters can be estimated. The PK population will be the primary population for the PK analysis.

12.3.1.2. Subject Demographic and Disposition Data

Subject disposition will be presented for all subjects. The number of subjects who completed the study and discontinued from the study will be provided. All pertinent subject demographics will be presented using descriptive statistics. The reasons for early discontinuation will be presented.

12.3.1.3. Analysis of Safety Variables

AEs will be mapped to a Medical Dictionary for Regulatory Activities (MedDRA) preferred term (PT) and system organ classification (SOC). Any event reported on the subject's study record that occurs on or after the initiation of study drug is defined as treatment emergent. Additionally, it is assumed that an AE that is reported to have started on Day 1 of a given treatment period without an associated onset time may have occurred after the initiation of study drug. Hence, AEs occurring on Day 1 with no associated onset time will be assumed to be treatment emergent. The occurrence of TEAEs will be summarized by cohort and treatment assignment using MedDRA PTs, SOCs, and severity. Separate summaries of treatment-emergent SAEs and AEs considered to be related to study drug will be generated. All AEs will be listed for individual subjects showing both verbatim and preferred terms.

Descriptive summaries of vital signs, ECG parameters (12 lead and telemetry), ECHOs, and clinical laboratory results will be presented separately for each cohort by study visit and treatment assignment. Laboratory abnormalities will be graded according to the modified DMID criteria ([APPENDIX A](#)).

Any graded abnormality that occurs following the initiation of study drug and represents at least one grade increase from the baseline assessment is defined as treatment emergent. The number and percentage of subjects experiencing treatment-emergent graded toxicities will be summarized by treatment group. Laboratory toxicity shifts from baseline to post-baseline assessments will be summarized by treatment group.

PE results will be presented in listings. Changes in PE results that are AEs will be reported in AE tables.

Concomitant medications will be coded using the World Health Organization (WHO) Dictionary. These data will be summarized by cohort and treatment assignment.

Subjects receiving placebo will be pooled and reported together across cohorts.

12.3.1.4. Pharmacokinetic Analysis

Concentrations of galidesivir will be determined by validated plasma and urine assays and will be summarized by treatment and displayed in figures. Plasma PK parameters for each subject will be estimated over the sampling interval using noncompartmental analysis (Phoenix WinNonlin Version 7.0 or higher, Certara) and summarized by treatment group using descriptive statistics. The amount and percentage of galidesivir excreted in the urine will be assessed at all doses. If possible, data will be summarized by cohort and dose proportionality assessed.

The PK parameters that will be estimated for galidesivir are listed in [Table 9](#). Additional analyses may be conducted as appropriate.

Table 9: Pharmacokinetic Parameters

Pharmacokinetic Parameter	Definition
AUC _{inf}	Area under the concentration versus time curve extrapolated to infinite time, calculated as AUC _{last} + (C _{last} /λ _z)
AUC _t	Area under the concentration versus time curve from time zero to time “t”; may be denoted as AUC _{last} if the “t” is the last timepoint with a measurable concentration
% AUC _{exp}	Percentage of AUC extrapolated between AUC _{last} and AUC _{inf}
C _{last}	Last measurable concentration of drug
C _{max}	Maximum observed concentration of drug
t _{1/2}	Estimate of the terminal elimination half-life of the drug
CL	CL = Dose/AUC where “Dose” is the dose of the drug and AUC = AUC _{inf}
λ _z	Terminal elimination rate constant, estimate by linear regression of the terminal elimination phase of the concentration of drug versus time curve
V _z	Volume of distribution of the drug
T _{max}	Time to C _{max}
CL _r	Renal clearance of unchanged drug in a specific interval (CL _r [interval]) or cumulatively over all collection intervals
% Dose _{excreted}	Percentage of given dose excreted in the urine as unchanged drug

In all derivations of PK parameters, zero will be substituted for concentrations below the quantitation limit (BQL) of the assay. Samples that are BQL, but are between two samples with detectable concentrations will be excluded from PK analysis.

